5.0 TREATMENT PLAN

5.1 Treatment Dosage and Administration

Protocol treatment must start within 14 business days of enrollment to the study.

5.1.1 Therapy will include pembrolizumab 200 mg IV starting on day 1 in 21 day cycles. Patients will receive 1 dose (cycle 1) of pembrolizumab and commence SBRT no later than initiation of cycle 2.

5.1.2 SBRT will be given to ≥ 1 metastatic lesion(s) deemed most appropriate for such therapy by the treating radiation oncologist. SBRT will be delivered in 3 or 5 fractions with dose and fractionation selected to respect standard normal tissue dose constraints for adjacent organs at risk. See section 5.3 for further details.

5.1.3 The lesion to which SBRT is given will be identified after the patient receives 1 dose of pembrolizumab

5.1.3 Patients will be treated with supportive care pre-medications as clinically indicated including anti-emetics.

REGIMEN DESCRIPTION					
Agent	Premedications	Dose	Route	Schedule	Cycle Length
Pembrolizumab	None mandated	200 mg	IV	Once every 21 days (+/- 3 business days)	
SBRT	None mandated	3-5 fractions with dose and fractionation selected to respect standard normal tissue dose constraints for the relevant organs in the vicinity of the target lesion(s).	n/a	In cycle 1 any time after D1 and will commence no later than initiation of cycle 2	

5.2 Toxicities and Dosing Delays/Dose Modifications

Any patient who receives one dose of pembrolizumab will be evaluable for toxicity. Each patient will be assessed for the development of toxicity according to the Time and Events Table (Section 6.4). Toxicity will be assessed according to the NCI Common Terminology Criteria for Adverse Events (CTCAE), version 4.03. Dose adjustments should be made according to the system showing the greatest degree of toxicity.

Dose modifications in strength are not permitted for pembrolizumab

Dosing delays for Pembrolizumab:

- No dose delays for pembrolizumab are needed for hematologic changes.

- With any grade 2 or higher **non-hematologic toxicity deemed to be related to pembrolizumab**, hold pembrolizumab and refer to section 5.2.1. If adverse event is not an event of interest and improves to grade 1 or better, pembrolizumab may be resumed.
- If non-hematologic toxicity does not improve to grade 1 or better in 12 weeks from prior dose, discontinue pembrolizumab.

5.2.1 **Events of interest for Pembrolizumab:**

Certain adverse events that are possibly immune mediated warrant special monitoring and management, and are outline below to guide investigators.

5.2.1.1 **Pulmonary:**

Rule out non-inflammatory causes. If non-inflammatory cause, treat accordingly and continue protocol therapy. Evaluate with imaging and pulmonary consultation.

Grade of pneumonitis (NCI CTCAE v4.03)	Management	Follow-up
Grade 1 Radiographic Changes Only	
 • Consider delay of pembrolizumab • Monitor for symptoms every 2-3 days • Consider pulmonary and infectious disease consultations 	
 • Re-image at least every 3 weeks • If worsening, treat as grade 2, 3 or 4
Grade 2 Mild to moderate new symptoms	
 • Delay pembrolizumab • Consult pulmonary and infectious disease • Monitor symptoms daily, consider hospitalization • 1.0mg/kg/day methylprednisolone IV or oral equivalent • Consider bronchoscopy and/or lung biopsy 	
 • Re-image every 1-3 days • Consider prophylactic antibiotics while on steroids • If improves: 
 • When symptoms return to near baseline, taper steroids over at least one month • When steroids are at 10mg oral prednisone (or equivalent) or below, resume pembrolizumab • If not improving after 2 weeks or worsening, treat as grade 3 or 4
Grade 3 or 4 Severe new symptoms and/or new or worsening hypoxia	
 • Discontinue pembrolizumab • Hospitalize • Consult pulmonary and infectious disease • 1-2mg/kg/day methylprednisolone IV or IV equivalent • Add prophylactic antibiotics for opportunistic infections like PCP • Consider bronchoscopy and/or lung biopsy 	
 • If improves to baseline: 
 • Taper steroids for at least 6 weeks • If not improving after 48 hours or worsening 
 • Add additional immunosuppressive agent(s) (e.g. infliximab, cyclophosphamide, intravenous immunoglobulin or

5.2.1.2 Gastrointestinal:

Rule out non-inflammatory causes. If non-inflammatory cause, treat accordingly and continue protocol therapy. Opiates or narcotics may mask symptoms of perforation. Infliximab should not be used in case of perforation or sepsis.

Grade of diarrhea/colitis (NCI CTCAE v4.03)	Management	Follow-up
Grade 1 
 Diarrhea of less than 4 stools per day over baseline or asymptomatic colitis 	
 Continue pembrolizumab Symptomatic treatment such as loperamide 	
 Close monitoring for worsening symptoms Educate patient to report worsening immediately If worsening, treat as grade 2,3 or 4
Grade 2 
 Diarrhea of 4-6 stools per day over baseline OR IV fluids needed < 24 hours due to diarrhea OR Colitis with abdominal pain or blood in stool 	
 Delay pembrolizumab Administer corticosteroids (initial dose of 1 to 2 mg/kg/day prednisone or equivalent followed by a taper) Consider prophylactic antibiotics for opportunistic infections like PCP if steroid treatment prolonged 	
 If improves to grade 1, resume pembrolizumab Resume pembrolizumab if the event improves to grade 0 or 1 within 12 weeks and corticosteroids have been reduced to the equivalent of ≤ 10mg oral prednisone per day When symptoms improve to grade 1, taper steroids over at least one month If worsening, treat as grade 3 or 4
Grade 3 
 Diarrhea ≥ 7 stools per day over baseline OR IV fluids needed for ≥ 24 hours due to diarrhea OR Colitis with severe abdominal pain or medical intervention indicated 	
 Delay pembrolizumab 1-2mg/kg/day methylprednisolone IV or IV equivalent Start prophylactic antibiotics for opportunistic infections such as PCP Consider lower endoscopy 	
 If improves 
 Continue steroids until symptoms are grade 1, then taper over at least one month Resume pembrolizumab if the event improves to grade 0 or 1 within 12 weeks and corticosteroids have been reduced to the equivalent of ≤ 10mg oral prednisone per day If persists for >3-5 days or recurs after improvement, add infliximab 5mg/kg if no contraindication (Note: infliximab should not be used in cases of perforation or sepsis)
Grade 4 Life threatening or perforation	
 Discontinue pembrolizumab 1-2mg/kg/day methylprednisolone IV or IV equivalent Start prophylactic antibiotics for opportunistic infections such as PCP Consider lower endoscopy 	
 If improves 
 Continue steroids until symptoms are grade 1, then taper over at least one month If persists for >3-5 days or recurs after improvement, add infliximab 5mg/kg if no contraindication (Note: infliximab should not be used in cases of perforation or sepsis)

5.2.1.3 Endocrinopathy:

Rule out non-inflammatory causes. If non-inflammatory cause, treat accordingly and continue protocol therapy. Consider visual field testing, endocrinology consultation and imaging.

Endocrinopathy	Management	Follow-up
Asymptomatic thyroid-stimulating hormone (TSH) elevation	
 Continue pembrolizumab If TSH <0.5 x LLN or TSH >2x ULN, or consistently out of range in subsequent measurements, include free T4 in subsequent measurements as clinically indicated Consider endocrinology consult 	
Symptomatic Hypothyroidism	
 Initiate thyroid replacement 	
Symptomatic Hyperthyroidism	
 Delay pembrolizumab Consider endocrinology consult Initiate anti-thyroid drug 	
 Resume pembrolizumab when symptoms of hyperthyroidism are controlled and thyroid function is improving
Hypophysitis	
 Administer corticosteroids and hormone replacement as clinically indicated Delay pembrolizumab for grade 2 or 3 hypophysitis Permanently discontinue pembrolizumab for grade 4 hypophysitis 	
Symptomatic Adrenal Insufficiency	
 Delay pembrolizumab Administer methylprednisolone 1-2 mg/kg/day IV followed by oral prednisone 1-2mg/kg per day or equivalent once symptoms improve Add prophylactic antibiotics for opportunistic infections 	
 If improves to \leq grade 1, taper steroids over at least one month Resume pembrolizumab if the event improves to grade 0 or 1 within 12 weeks and corticosteroids have been reduced to the equivalent of \leq10 mg oral prednisone per day and the patient is on stable replacement therapy if required

5.2.1.4 Hepatic:

Rule out non-inflammatory causes. If non-inflammatory cause, treat accordingly and continue protocol therapy. Consider imaging for obstruction.

Grade of Liver Test Elevation (NCI CTCAE v4.03)	Management	Follow-up
Grade 1 AST or ALT >ULN to 3x ULN and/or total bilirubin >ULN to 1.5x ULN	
 Continue pembrolizumab 	
 Continue liver function test monitoring per protocol If worsening, treat as grade 2,3, or 4
Grade 2 AST or ALT >ULN to 3-5x ULN and/or total bilirubin >ULN to 1.5-3x ULN	
 Delay pembrolizumab Administer corticosteroids at a dose of 1-2mg/kg/day oral prednisone 	
 Resume pembrolizumab if returns to baseline If persists >5-7 days or worsens, treat as grade 3 or 4

Grade 3 or 4 AST or ALT >5x ULN and/or total bilirubin >3x ULN	
 Discontinue pembrolizumab Increase frequency of monitoring to every 1-2 days 1-2mg/kg/day methylprednisolone IV or IV equivalent for grade 3 and 2 mg/kg/day methylprednisolone IV for grade 4 Add prophylactic antibiotics for opportunistic infections like PCP Consult gastroenterologist 	
 If improves to grade 2, taper steroids over at least one month If does not improve within 3-5 days or worsens after improvement: 
 Add mycophenolate mofetil 1g twice daily If no response within an additional 3-5 days, consider other immunosuppressive agents per local guidelines
---	--	---

5.2.1.5 Pancreatic:

Rule out non-inflammatory causes. If non-inflammatory cause, treat accordingly and continue protocol therapy. Consider imaging for obstruction.

Grade of pancreatic toxicity (NCI CTCAE v4.03)	Management	Follow-up
Grade 1-2 Amylase or Lipase up to 2x ULN	
 Continue pembrolizumab 	
Grade 2 or 3 Pancreatitis or Grade 3 serum amylase or lipase level (>2x ULN)	
 Delay or pembrolizumab Treat with 1-2mg/kg IV methylprednisolone or equivalent per day 	
 Once symptoms improve, follow with 1-2mg/kg of oral prednisone or equivalent per day Resume pembrolizumab if amylase/lipase improves to ≤ grade 1 within 12 weeks, symptoms of pancreatitis have resolved, and corticosteroids have been reduced to ≤ 10 mg oral prednisone or equivalent per day
Grade 4 or recurrent pancreatitis	
 Discontinue pembrolizumab Treat with 1-2mg/kg IV methylprednisolone or equivalent per day 	
 Once symptoms improve, follow with 1-2mg/kg of oral prednisone or equivalent per day and taper for ≥ 1 month

5.2.1.6 Neurological:

Rule out non-inflammatory causes. If non-inflammatory cause, treat accordingly and continue protocol therapy.

Grade of neurological toxicity (NCI CTCAE v 4.03)	Management	Follow-up
Grade 1 
 Asymptomatic or mild symptoms Intervention not indicated 	
 Continue pembrolizumab 	
 Continue to monitor the patient, if worsening treat as grade 2, 3, or 4

Grade 2
 
 Moderate symptoms Limiting instrumental ADLs 	
 Delay pembrolizumab Treat symptoms per institutional guidelines Consider 0.5-1mg/kg per day methylprednisolone IV or oral equivalent 	
 If returns to baseline, resume pembrolizumab If worsens, treat as grade 3 or 4

Grade 3 or 4
 
 Severe symptoms Limiting self-care ADLs 	
 Discontinue pembrolizumab Consult Neurology Treat symptoms per institutional guidelines 1-2mg/kg per day IV methylprednisolone or IV equivalent Add prophylactic antibiotics for opportunistic infections 	
 If improves to grade 2, taper steroids over at least one month If worsens, consider IVIG or other immunosuppressive therapies per institutional guidelines

Meningitis or Encephalitis
	
 Discontinue pembrolizumab 1-2mg/kg per day IV methylprednisolone or IV equivalent Add prophylactic antibiotics for opportunistic infections 	
 If improves, convert to oral steroids (prednisone 60mg/day or equivalent) When symptoms improve to \leq grade 1, taper steroids over at least one month

5.2.1.6 Skin:

Rule out non-inflammatory causes. If non-inflammatory cause, treat accordingly and continue protocol therapy

Grade of Rash (NCI CTCAE v4.03)	Management	Follow-up

Grade 1-2 Covering \leq 30% body surface area (BSA)
	
 Symptomatic therapy (such as antihistamines, topical steroids) Continue pembrolizumab 	
 If persists 1-2 weeks or recurs 
 Consider skin biopsy Delay pembrolizumab Consider 0.5-1mg/kg/day methylprednisolone IV or oral equivalent Once improving, taper steroids for at least one month Consider prophylactic antibiotics for opportunistic infections like PCP Resume pembrolizumab if rash improves to \leq grade 1 within 12 weeks and corticosteroids have been reduced to \leq 10 mg oral prednisone or equivalent per day If worsens, treat as grade 3 or 4

Grade 3-4 Covering $>$30% BSA or life threatening consequences
	
 Delay or discontinue pembrolizumab Consider skin biopsy If patient is diagnosed with Stevens-Johnson Syndrome (SJS) or Toxic Epidermal Necrolysis (TEN), pembrolizumab must be discontinued Consult dermatology 	
 If improves to grade 1: 
 Taper steroids over at least one month Resume pembrolizumab if rash improves to \leq grade 1 within 12 weeks and corticosteroids have been reduced to \leq 10 mg oral prednisone or equivalent per day

	
 • 1-2mg/kg/day methylprednisolone IV or IV equivalent • Add prophylactic antibiotics for opportunistic infections 	
--	--	--

5.2.1.7 Renal:

Rule out non-inflammatory causes. If non-inflammatory cause, treat accordingly and continue protocol therapy

Grade of elevation in serum creatinine (NCI CTCAE v4.03)	Management	Follow-up
Grade 1 Serum creatinine >ULN and >baseline but ≤1.5x baseline	
 • Continue pembrolizumab • Monitor serum creatinine weekly 	
 • If returns to baseline, resume creatinine monitoring per protocol • If worsens, treat as grade 2, 3, or 4
Grade 2 or 3 Serum creatinine 1.5x baseline to ≤ 6 x ULN	
 • Delay or discontinue pembrolizumab • Monitor serum creatinine every 2-3 days • 0.5-1 mg/kg/day methylprednisolone IV or oral equivalent • Add prophylactic antibiotics for opportunistic infections • Consider renal biopsy 	
 • If improves to grade 1 
 • Taper steroids over at least one month • Resume pembrolizumab if improves to ≤ grade 1 within 12 weeks and corticosteroids have been reduced to ≤ 10 mg oral prednisone or equivalent per day • If elevation persists >7 days or worsens, treat as grade 4
Grade 4 Serum creatinine <6x ULN	
 • Discontinue pembrolizumab • Monitor serum creatinine daily • 1-2mg/kg/day methylprednisolone IV or IV equivalent • Add prophylactic antibiotics for opportunistic infections • Consult nephrology • Consider renal biopsy 	
 • If improves to grade 1 
 • Taper steroids over at least one month • Resume pembrolizumab if improves to ≤ grade 1 within 12 weeks and corticosteroids have been reduced to ≤ 10 mg oral prednisone or equivalent per day

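### The grade 2 diarrhea/colitis row gives two conflicting rules for resuming pembrolizumab, one without a steroid limit, and does not say which governs

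*Combined protocol and SAP*

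**What the plan says.** Section 5.2.1.2 (Gastrointestinal) tells the investigator to delay pembrolizumab for grade 2 diarrhea or colitis and to give corticosteroids: "initial dose of 1 to 2 mg/kg/day prednisone or equivalent followed by a taper". Three bullets in the follow-up cell of that row matter here:

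- first: "If improves to grade 1, resume pembrolizumab";
- second: "Resume pembrolizumab if the event improves to grade 0 or 1 within 12 weeks and corticosteroids have been reduced to the equivalent of" 10 mg or less of oral prednisone per day;
- third: "When symptoms improve to grade 1, taper steroids over at least one month".

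The grade 3 row of the same table carries only the second, steroid-limited rule. Section 5.2.1 introduces all of these tables by saying that the events "warrant special monitoring and management, and are outline below to guide investigators".

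**The concern.** The first two bullets answer the same question, when to re-expose the patient, with different conditions. Reaching grade 1 triggers resumption under the first bullet and the start of the taper under the third. Read literally, the first bullet permits a dose of pembrolizumab while the patient is still on, or close to, the full steroid dose. The second bullet forbids that.

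The protocol does not explain the 10 mg threshold. The natural inference is that it is there to show that improvement holds on little steroid before the drug is given again. Under the first bullet, the patient can be re-dosed while improvement may still depend on a much higher dose. The less severe grade then has the looser literal rule, since grade 3 has no such route.

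Two investigators could re-dose similar patients weeks apart, each able to point to a written instruction, and a monitor would have no clear basis for calling either a deviation.

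**Working it through.** There is no planned figure to reproduce. The check compares texts, with arithmetic only to show how far apart the two rules lie.

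**1. Does other text settle precedence?**

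- The general resume rule in Section 5.2 applies only to events that are not events of interest, so it does not reach this row.
- The 12-week discontinuation rule in Section 5.2 limits time to improvement and says nothing about steroid dose.
- The Section 5.2 instruction to adjust by the most severely affected system chooses between organ systems, not between bullets.
- The 10 mg ceiling in Section 5.4 exempts steroids given to manage adverse events.

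None of these decides the matter.

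**2. Is this row an exception?** Ten other rows in Section 5.2.1 mention a systemic steroid and state a resume rule:

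| Resume rule | Rows | Count |
|---|---|---|
| Has the 10 mg limit | Pneumonitis grade 2; GI grade 3; adrenal insufficiency; pancreatic grade 2 or 3; skin grade 1-2; skin grade 3-4; renal grade 2 or 3; renal grade 4 | 8 |
| No steroid limit, but return to baseline required | Hepatic grade 2; neurological grade 2 | 2 |

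The pneumonitis row is typical of the first group: "When steroids are at 10mg oral prednisone (or equivalent) or below, resume pembrolizumab". The two rows in the second group read "Resume pembrolizumab if returns to baseline" (hepatic) and "If returns to baseline, resume pembrolizumab" (neurological). Only the GI grade 2 row allows resumption at residual grade 1 with no steroid limit.

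**3. How far apart are the rules?** From the protocol: 1 to 2 mg/kg/day, a 10 mg limit, a taper of at least one month and 21-day cycles. Assumed: weight 50 to 100 kg, the taper shape, a linear taper lasting 28 to 30 days, and grade 1 reached on day 10 with the next dose due on day 21.

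- *On the day grade 1 is reached:* 50 kg × 1 mg/kg = 50 mg/day to 100 kg × 2 mg/kg = 200 mg/day. Divided by 10 mg, that is 5 to 20 times the limit.
- *At the next scheduled dose,* 21 − 10 = 11 days into the taper:
  - Linear taper to zero over T days from dose D, D × (1 − 11/T): 50 × (1 − 11/28) = 30.4 mg to 200 × (1 − 11/30) = 126.7 mg, or 3.0 to 12.7 times the limit.
  - Halving weekly, one halving done: 25 to 100 mg, or 2.5 to 10 times the limit.
- *Wait from grade 1 until the second bullet is met:*
  - Linear, T × (1 − 10/D): 28 × (1 − 10/50) = 22.4 days to 30 × (1 − 10/200) = 28.5 days.
  - Halving weekly: from 50 mg, three halvings reach 6.25 mg on day 21; from 200 mg, five halvings reach 6.25 mg on day 35.

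The first bullet allows re-dosing at once on reaching grade 1. The second defers it by about three to five weeks under these assumptions.

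**The case against.** The strongest reply is that the bullets can both be satisfied. The first sets no deadline, so an investigator who waits for the second breaks nothing. On that reading the first is a loose summary and the second supplies the conditions. Most clinicians would probably apply the stricter line, and the tables are offered as guidance. That makes harm less likely, but it does not settle the text. The first bullet is worded as a complete instruction to resume, and an investigator who acts on it has followed the protocol. Nor can it be confined to patients not on steroids, because the row orders steroids and has no steroid-free branch.

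Other points stand in part:

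- The trial has 20 patients at one center and the documents give no rate of grade 2 colitis, so few patients may be affected. Quarterly safety review (Section 12.0) helps with oversight but does not resolve the wording.
- The hepatic grade 2 row orders 1 to 2 mg/kg/day of prednisone and has no steroid limit either. Return to baseline on full-dose prednisone may also depend on the steroid. That row deserves the same look.
- The renal grade 4 row, counted above among those with the limit, tells the investigator to discontinue and then gives a resume rule. Leaving it out makes the count seven of nine, and the GI grade 2 row is still the exception.
- The multiples are illustrative. They show mainly that 1 to 2 mg/kg/day is far above 10 mg.

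**Conclusion.** The concern holds. One cell contains two rules for resuming pembrolizumab that differ on steroid dose, and nothing in the protocol says which governs. Followed literally, the first permits re-dosing at 5 to 20 times the second rule's steroid limit on the day grade 1 is reached, and at about 2.5 to 13 times the limit 11 days into a taper. These ranges rest on the assumed weights, taper shapes and timing. The conflict itself rests only on the text.

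This is a flaw in safety instructions, not an error in the statistical design. The number of patients it would touch is unknown, and no effect on the primary endpoint is claimed. It is worth correcting because it governs re-exposure after immune-mediated colitis and the correction is small.

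**What to change.** Delete the first follow-up bullet in the grade 2 diarrhea/colitis row and keep the second. Grade 2 then uses the same resume rule as grade 3, and no new policy is created. The clinical team should confirm this. At the same time it should check whether the missing steroid limit in the hepatic and neurological grade 2 rows is intended, and whether the renal grade 4 row should state a resume rule at all.

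The drafting cost is one bullet in one table cell. The clinical cost is a longer hold for some patients: about 22 to 28 days from reaching grade 1 under the assumed linear taper, or 21 to 35 days with weekly halving, and more if the taper runs beyond a month. A longer hold also uses part of the 15-week window for the primary endpoint. Without delays, dose 4 falls 3 × 21 = 63 days after the first dose and the window closes at 15 × 7 = 105 days. That leaves 42 days of slack if success means four doses given (Section 2.4), or 105 − 84 = 21 days if it means four full cycles (Section 11.1).

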3.1 Inclusion Criteria

- 3.1.1 Subjects must have a histologic diagnosis of urothelial carcinoma
- 3.1.2 Subjects must have radiologic evidence of metastatic disease with measurable disease by RECIST 1.1 criteria other than the target lesion(s) for SBRT
- 3.1.3 Subjects must have at least 1 metastatic lesion previously not radiated that is amenable to SBRT per treating radiation oncologist.
- 3.1.4 Subjects must have had progression of disease within 12 months of platinum-containing chemotherapy (chemotherapy could have been given in the neoadjuvant, adjuvant or metastatic setting) for urothelial cancer
- 3.1.5 ECOG performance status of 0 to 2
- 3.1.6 Absolute neutrophil count of $\geq 1000/\text{mm}^3$, platelet count $\geq 100,000/\text{mm}^3$, hemoglobin ≥ 8.0 g/dl; total bilirubin/ALT/AST < 2.5 x upper limit of normal (patients with known gilbert disease who have serum bilirubin ≤ 3 x ULN may be enrolled); serum creatinine < 3.0 mg/dl or if elevated, a calculated estimated glomerular filtration rate (eGFR) of ≥ 30 mL/min/1.73 m²
- 3.1.7 Subjects must have recovered to baseline or \leq grade 1 CTCAE v 4.03 from toxicities related to any prior treatments unless AE(s) are clinically non-significant and/or stable on supportive therapy
- 3.1.8 Subjects must be ≥ 2 weeks from most recent systemic therapy or most recent radiation therapy
- 3.1.9 Women of childbearing potential must have a negative serum or urine pregnancy test within 28 days prior to registration. Women of non-childbearing potential are defined as those who have no uterus, ligation of the fallopian tubes, are naturally postmenopausal for at least 12 consecutive months or have undergone surgical removal of the ovaries. Women of childbearing potential should use highly effective contraception during treatment and for 6 months after the last dose of pembrolizumab
- 3.1.10 Age ≥ 18 years

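### Section 5.2.1.4: the hepatic grade 1 and grade 2 rows share a printed lower bound, so a mild elevation meets two rows with opposite instructions

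*Combined protocol and SAP*

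**What the plan says.** Section 5.2.1.4 (Hepatic) sorts liver test elevations into three rows, under a header that names CTCAE v4.03.

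- Grade 1: "AST or ALT >ULN to 3x ULN and/or total bilirubin >ULN to 1.5x ULN". Action: "Continue pembrolizumab".
- Grade 2: "AST or ALT >ULN to 3-5x ULN and/or total bilirubin >ULN to 1.5-3x ULN". Actions: "Delay pembrolizumab" and "Administer corticosteroids at a dose of 1-2mg/kg/day oral prednisone". Follow-up: "If persists >5-7 days or worsens, treat as grade 3 or 4".
- The combined row for the two highest grades reads: "AST or ALT >5x ULN and/or total bilirubin >3x ULN". The first action listed is to discontinue the drug.

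Section 5.2 holds pembrolizumab for non-hematologic toxicity of grade 2 or above that is judged related to it, and sends the reader to section 5.2.1 for the detail. It names CTCAE v4.03 for grading. The documents do not reproduce that scale's liver cut-offs anywhere else. Section 3.1.6 sets the entry limit as "total bilirubin/ALT/AST < 2.5 x upper limit of normal", with a separate allowance for bilirubin in Gilbert disease.

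**The concern.** The two rows give opposite instructions, and the printed numbers do not separate them. Both begin just above ULN, for AST/ALT and for bilirubin. The grade 2 upper bound is also unclear, because a range stands where a single number belongs.

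This is an operative rule on holding drug and starting steroids, not background text. Someone who follows the printed range could hold the drug for a value that the row above says to treat through. If the value then stays raised beyond 5-7 days, the grade 2 follow-up moves the patient to the row that ends pembrolizumab. Two clinicians with the same laboratory report could act differently and both cite the protocol. The primary endpoint counts pembrolizumab doses given within a fixed window, so inconsistent holds would also add noise to the feasibility result.

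**Working it through.** The plan states no figure to reproduce. The check is a comparison of the printed ranges, in multiples of ULN.

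**Inputs (section 5.2.1.4)**

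- Grade 1: AST/ALT above 1 to 3; bilirubin above 1 to 1.5.
- Grade 2 as printed: lower bound above 1 for both analytes; upper bound 3 or 5 for AST/ALT and 1.5 or 3 for bilirubin, depending on which end of the printed range is used.
- Grade 3 or 4: AST/ALT above 5; bilirubin above 3.

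**Overlap as printed.** The overlap runs from the larger lower bound to the smaller upper bound.

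- AST/ALT, grade 2 upper bound 3: overlap 1 to 3, so (3 − 1)/(3 − 1) = 100% of grade 1. Gap before grade 3: 5 − 3 = 2x ULN.
- AST/ALT, upper bound 5: overlap 1 to 3, again 100%. Gap: 5 − 5 = 0.
- Bilirubin, upper bound 1.5: overlap 1 to 1.5, so (1.5 − 1)/(1.5 − 1) = 100%. Gap: 3 − 1.5 = 1.5x ULN.
- Bilirubin, upper bound 3: overlap 1 to 1.5, again 100%. Gap: 3 − 3 = 0.

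Whichever upper bound is taken, grade 2 contains all of grade 1. AST at 2x ULN is a plain example of a value that meets both rows.

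**Alternative reading.** Suppose the leading words of the grade 2 ranges are a leftover, and 3-5x and 1.5-3x are the whole ranges. The overlap with grade 1 is then nil apart from the shared end points at 3x and 1.5x, and there is no gap before grade 3. This tests consistency with the neighbouring rows only. It does not establish which thresholds are right.

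**Is there a tie-break?** Section 5.2 says that dose adjustments follow the organ system with the worst toxicity. That ranks systems against each other; it does not choose between two rows of one table. If a reader applied it by analogy, it would point to the higher row, that is, to the hold.

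**Reach into the primary endpoint (sections 2.4, 5.1 and 11.1)**

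- Window: 15 × 7 = 105 days from the first dose.
- Dose 4 on schedule: 3 × 21 = 63 days after dose 1. Slack: 105 − 63 = 42 days.
- This counts doses, as section 2.4 does. Section 11.1 speaks of completing 4 cycles. If that included the full 21 days of cycle 4, the slack would be 105 − 4 × 21 = 21 days.
- A patient who discontinues before dose 4 counts as a failure, because one dose makes a patient evaluable (sections 5.10 and 11.1), unless a complete response came before SBRT.
- One such patient among 20 moves the result by 1/20 = 5 percentage points. At the 14/20 threshold that is 70% against 13/20 = 65%.

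The documents give no rate of new mild liver test elevations, so the expected number of patients affected cannot be calculated.

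**The case against.** The best reply is that the intended ranges can be read off the same table. The figures 3-5x and 1.5-3x exactly fill the space between grade 1 and grade 3. The grade 1 follow-up treats grade 2 as a worsening, which makes sense only if grade 2 lies above grade 1. Section 5.2 ties the hold to the assigned grade under a named scale, and section 5.2.1 offers its tables as guidance. An event graded 1 would go to the grade 1 row. This stands as evidence of a drafting slip, and it limits the severity. It does not make the printed rows consistent, because the reader must decide which printed words to ignore and the cut-offs are not restated elsewhere.

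A reader might infer three stronger claims that the documents do not support.

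- **Patients enter the trial already subject to a hold.** The entry limit of 2.5x ULN does fall inside the AST/ALT overlap. But section 8.1 classes abnormalities that began before treatment as pre-existing, and only a worsening counts as an adverse event. Section 5.2 requires the toxicity to be judged related to pembrolizumab. The hepatic section first asks for non-inflammatory causes to be excluded, and lets therapy continue where one is found. A stable baseline elevation is therefore largely covered.
- **A needed hold will be missed.** The slip extends grade 2 downward, so the likely error is an extra hold. A missed hold arises only if the upper bound is read as 3x or 1.5x, which leaves the gaps shown above.
- **The 15-week endpoint is compromised.** A short hold fits within the slack. Failure by this route needs a literal reading, attribution to the drug, and either persistence that leads to discontinuation or a long delay.

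**Conclusion.** The point holds as an internal contradiction in one table. As printed, the grade 2 row covers 100% of the grade 1 row for both analytes, with opposite instructions, and the grade 2 upper bound is ambiguous. The most likely practical effect is an unnecessary hold, with steroids, for a new mild elevation attributed to pembrolizumab. Discontinuation is possible if the literal reading is followed beyond 5-7 days.

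The effect on the primary result is conditional and probably small: nothing for a short hold, and 5 percentage points for each evaluable patient who discontinues before dose 4 for this reason. This assumes 21-day cycles on schedule and 20 evaluable patients. The correction is worth making because the rule governs drug holds and steroid use, not because the feasibility conclusion is shown to be at risk.

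**What to change.** The clinical team should reconcile the grade 1 and grade 2 cells of section 5.2.1.4 with each other, with the grade 3 or 4 row and with the grading scale named in the header. Each AST, ALT or bilirubin value should fall in one row only. Each row should have a single lower and a single upper limit per analyte, and the table should say which row owns a value exactly on a cut-off. No threshold or management rule is proposed here.

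The cost is the correction of one table cell, or at most two, in an amendment. Sample size, endpoints and analysis are unchanged. If patients have already been treated, the study team could check whether any hold or discontinuation for a liver test elevation followed the overlapping range.
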